Title of study

Wearable Monitoring Systems for Swallowing Function and Disorders

NCT #

NCT04243577

Latest Approval Date

10/18/2023

Study Protocol & Statistical Analysis Plan

STUDY PROTOCOL

Objective

Wearable tele-rehabilitation technology allows for the efficient provision of rehabilitation services from a distance, facilitating tele-management of many disorders. The proposed research aimed to develop and validate a mechanically compliant, easy-to-use, and inexpensive wearable tele-monitoring system, for future use in the rehabilitation of swallowing disorders (dysphagia). The hypothesis was that the newly developed surface electromyographic (sEMG) wearable sensors would have equal or better performance than traditional wired sEMG sensors used today in clinical practice. Factors related to signal quality and patient reported outcomes (e.g., satisfaction/comfort level, adverse effects etc.) were examined.

Design and Devices

This study is a within subject randomized cross-over design study. Two iterations of a wearable surface EMG sensors patch we developed were tested against commercially available wired devices. The first iteration of the wearable sensor patch was an ultrathin patch with a honeycomb-inspired design that included sEMG and strain sensors in order to capture muscle activity and thyroid movement signals from the submental area during swallows and swallow maneuvers/exercises. The second iteration was a more durable slightly thicker flexible, non-stretchable, and double-sided thin patch. The exact same methods were used to test both iterations against commercially available conventional sensors. For both iterations' testing, the order of the experimental conditions differed across groups. Group A participants completed the experimental protocol with the conventional electrodes first, and Group B participants completed the protocol with the experimental patch first. There was a 10-min rest period between the two experimental conditions.

The first iteration testing was completed in 40 healthy older adults. Results revealed technical improvements were needed and therefore a second improved version of the sensor was then developed. The second iteration testing was done in an additional sample of 30 healthy older adults. A total of 70 healthy older participants were included in the study.

Methods

Participants

Healthy older adults 50-85 years old (the typical age range of our target clinical population for future studies) were recruited in this study. Inclusion criteria were: 1) no history of dysphagia, 2) no history of neurological disease, head/neck cancer, radiation or surgery, 3) a score in the normal/mild range on the Montreal Cognitive Assessment (MoCA), and 4) a score of <3 on the Eating Assessment Tool (EAT-10; a self-report screening for dysphagia). Exclusion criteria were: 1) history of dysphagia; 2) history of neurological disease, head/neck cancer, radiation or surgery, 3) a score in moderate-severe range on MoCA, and 4) a score of >2 on the EAT-10.

Instrumentation Validation – Data Collection

For each iteration of the device, a group of participants was tested using the experimental device/sensors and the commercially available ones in counterbalanced order. Results were analyzed to allow design improvements before the next iteration was developed and tested. To validate each of the two iterations of the newly developed sEMG patch, we used wired electrodes (e.g., AED Brands, A snap-style pad) connected to a commercially available wireless amplifier (BioRadio, GLNeuroTech Inc.), as the comparison system. During this experiment, the electrodes were placed on the submental muscles (under the chin). The sEMG signals were sampled while subjects remained as still as possible and sat upright with the head in neutral

position. Participants were asked to complete several types of swallows multiple times. Each set of tasks was tested with one type of device first (conventional or experimental) and was repeated 10 min after the first set with the other type of device. For both types of devices, swallows were confirmed via a nasal airflow cannula to detect the swallow apnea (nasal airflow cessation), and an observer's button that was be pressed at swallow completion.

Outcome Measures and Data Analysis

Primary Outcome Variables – Signal Quality parameters

Signal quality outcomes tested across both iterations' tests included normalized task-related EMG amplitude (primary outcome), and signal to noise (S/N) ratio. Because task sEMG amplitudes vary among subjects (e.g., as a function of electrode impedance), we expressed amplitude in microvolts and normalized these values within subjects. For normalization, participants produce 3 trials of maximum lingual press, and we expressed the task-related EMG amplitudes as percentages of the amplitude of this criterion gesture. For analysis, research assistants blinded to sensor type conducted analyses using a custom MATLAB script.

Secondary Outcome Variables – Preclinical parameters

We examined adverse effects and safety by thoroughly inspecting participants' submandibular skin before and after each experiment. Specifically, we documented the incidence of skin irritations in the subjects. A visual inspection form including a binary scale (YES/NO) was devised by the investigators (no formal name) and was used by a rater who thoroughly inspected the participants' submandibular skin before and after each experiment. For any irritation or change in appearance YES was selected and the type of irritation was descriptively recorded (e.g., red skin). This form was completed by a rater who was not part of the data collection process and who was blinded to sensors type to avoid any bias. The number of YESs were used to calculate the incidence of these adverse effects in the sample. This inspection was completed immediately after removal of each sensor type and 5 minutes later as well.

Ease-of-use/comfort was examined using a survey (using a positive centered 5-point Likert scale) with questions about ease-of-use/comfort after each experiment with each device. This survey included statements related to the participants' ease-of-use/comfort during the experimental protocol (e.g., I was comfortable while the experimenter placed the sensors on my skin). The answers were rated on a 10-point scale (i.e., 1 = extremely uncomfortable, 10 = extremely comfortable). Higher values indicated better or higher satisfaction/ comfort scores. Total scores were compared across conditions/devices tested.

STATISTICAL ANALYSIS PLAN

The study was designed to have at least 80% power to detect a difference in the primary variables of interest, that is, SNR, and normalized mean amplitude of swallow trials. The sample size was determined via a power analysis based on pilot results. Alpha level was set to .025 to correct for multiple comparisons. Quantile-quantile plots and the Shapiro-Wilk test was also used to assess normality. For S/N ratio comparisons non-inferiority tests were used for both iterations' testing. For the normalized amplitude data, equivalency testing was used for both iterations' testing. Margins for these tests were calculated using our preliminary data acquired with the conventional electrodes, which were considered as the current gold standard. Descriptive statistics (frequency counts) were used to report adverse effects (skin related effects). Paired t tests were used to test for differences in satisfaction/comfort level.

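### Does the mismatch over which outcome is primary leave the .025 level short of controlling error across the two patch versions?

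*Combined protocol and SAP*

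**What the plan says.** The protocol part, under Outcome Measures and Data Analysis, has the heading "Primary Outcome Variables – Signal Quality parameters". The sentence below it names "normalized task-related EMG amplitude (primary outcome), and signal to noise (S/N) ratio". Adverse skin effects and comfort come later under a separate heading for secondary outcomes; S/N ratio is not among them.

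The Statistical Analysis Plan bases power on the "primary variables of interest, that is, SNR, and normalized mean amplitude of swallow trials". It then says "Alpha level was set to .025 to correct for multiple comparisons", without giving the overall level, the comparisons counted or the sidedness. The tests are set out as "For S/N ratio comparisons non-inferiority tests were used for both iterations" and "For the normalized amplitude data, equivalency testing was used for both iterations".

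Design and Devices explains why there were two rounds. The first patch was tested in 40 people; "Results revealed technical improvements were needed and therefore a second improved version of the sensor was then developed". The second round used "an additional sample of 30 healthy older adults".

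**The concern.** Read literally, the parenthetical tag makes amplitude the only primary outcome, and the Statistical Analysis Plan makes it one of two. The outcomes have different tests and can disagree. If S/N ratio is non-inferior and amplitude is not equivalent, the Statistical Analysis Plan yields one positive primary result and the tag yields none. If amplitude is equivalent and S/N ratio fails, the tag yields a positive primary outcome and the Statistical Analysis Plan a split. No rule says how the two results combine into the hypothesis under Objective.

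The count of tests also changes. One outcome in two rounds is two tests; two outcomes in two rounds is four. A level of .025 looks like .05 divided by two, so it seems to cover two tests and not four. Because the second patch was built after the first fell short, the two rounds can look like two attempts at one hypothesis. The overall chance of a false claim would then be about double what a reader expects.

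**Working it through.** **Inputs.** Level .025 per test, and one non-inferiority and one equivalence test per round (Statistical Analysis Plan). Separate samples of 40 and 30 (Design and Devices), so the rounds are treated as independent. The overall .05 is an assumption. Margins and standard deviations are not given and are not needed for the error rates.

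**The plan's own figure.** .05/2 = .025. The divisor of two fits two outcomes within one round, and equally one outcome over two rounds.

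**Chance of at least one false primary claim, taking .025 as one-sided.** Equivalence by two one-sided tests at .025 has error of at most .025, so these are upper values for that test.

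| Reading | Formula | Result |
|---|---|---|
| Amplitude only, one round | .025 | 2.5% |
| Amplitude only, both rounds | 1 − .975² | 4.9% |
| Two outcomes, either counts, one round | at most 2 × .025 | 5.0% |
| Two outcomes, either counts, both rounds, tests independent | 1 − .975⁴ | 9.6% |
| Same, worst case within a round | 1 − .95² | 9.75% |
| Two outcomes, both required, one round | at most .025 | 2.5% |
| Two outcomes, both required, both rounds | at most 1 − .975² | 4.9% |

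The simple bound for four tests is 4 × .025 = 10%. With an assumed correlation between the two test statistics within a round, the four-test figure is 8.9% at 0.5 and 7.7% at 0.8.

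**If .025 was two-sided.** Each one-sided test is at .0125. The error is at most 2 × .0125 = 2.5% per round and 1 − .975² = 4.9% over both rounds, even with four tests and either outcome counting.

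**What the high figure needs.** Only one combination exceeds 5%: both rounds as one family, one-sided .025, and success on any single test. The document states none of the three. On the first, the text points the other way: the data-collection section speaks of validating each version of the patch and of using results to improve the design before the next version. The two patches differ physically and were tested in different people.

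**Cost of guarding against it.** Four tests held to 5% overall would need .05/4 = .0125 each. The half-width of the paired interval is t(1−a, n−1)/√n in units of the standard deviation of the differences. From a = .025 to a = .0125 it grows from 0.320 to 0.369 at n = 40 (0.369/0.320 = 1.15) and from 0.373 to 0.432 at n = 30 (0.432/0.373 = 1.16).

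**The label itself.** Two places treat S/N ratio as primary: the plural heading directly over the list and the power statement. One parenthetical stands against them. Neither the tests nor the level change with the choice.

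**The case for a change.** The best case for a change is that the tag is specific and a heading is generic, so the tag cannot simply be read away. The two outcomes can split, and a reader then cannot tell from the document whether the study succeeded. Objective states one hypothesis, and Design and Devices describes one study of 70 people with a second round prompted by the results of the first; that is where a family of tests ought to be declared. Reconciling the label and showing a 97.5% interval beside the 95% one would need no new data.

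Part of this stands. The tag does conflict with the Statistical Analysis Plan, and the success rule, the sidedness, the comparisons behind .025 and the handling of the several swallow types are all unstated. These are details for the authors to report as they were set before the data were seen, with any later relabelling marked as post hoc. They do not show that an analysis is unsound. With S/N ratio and amplitude reported separately for each patch, a split result is visible whatever label is used. The wider interval answers only to a family spanning both patches. The document makes no claim of 5% control over that family, and experienced statisticians would differ on whether successive versions of a device belong in one.

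**Conclusion.** No change to the plan follows. The mismatch is a clerical slip in one parenthetical, accompanied by missing detail that can be supplied in reporting. With two primary outcomes and an assumed overall .05, the stated .025 holds at most 5% within each round; with amplitude alone it holds 4.9% over both. The range of 7.7% to 9.75% over both rounds is correct arithmetic, but it depends on the three unstated conditions together, and its lower end also on an assumed correlation. If .025 was two-sided, or both outcomes had to succeed, the error over both rounds is at most 4.9%. Stricter intervals, 15% to 16% wider, would be a matter of preference about the family and would not correct an error in the plan.

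### The skin-irritation incidence counts every visible change in appearance, so irritation cannot be read apart from harmless removal marks; tabulate by recorded type, inspection time and sensor

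*Combined protocol and SAP*

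**What the plan says.** Under Secondary Outcome Variables – Preclinical parameters, the safety outcome is introduced with the statement that "we documented the incidence of skin irritations in the subjects". The instrument is described as follows: "A visual inspection form including a binary scale (YES/NO) was devised by the investigators (no formal name"). The rule for a positive score is: "For any irritation or change in appearance YES was selected and the type of irritation was descriptively recorded (e.g., red skin"). The numerator is then given: "The number of YESs were used to calculate the incidence of these adverse effects in the sample". On timing: "This inspection was completed immediately after removal of each sensor type and 5 minutes later as well". The rater is described as independent of data collection and unaware of sensor type.

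The Statistical Analysis Plan section adds only that adverse effects, under a broad label of skin-related effects, are reported as counts. It plans no comparison of sensors for this outcome. Neither section says which recorded descriptions count as irritation, how the two post-removal inspections combine, or whether a change that has cleared by 5 minutes still counts.

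**The concern.** The named outcome and the scored event are not the same thing. Irritation is a reaction of the skin. A change in appearance can also be a pressure imprint or adhesive residue. Under the rule as written, each of these earns the same YES as a reaction, and the incidence is built from YESs with no stated filter on type. The inspection made straight after removal is where such marks would be most likely to be seen, if they occur at all.

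The figure's use is comparative even without a test. Each participant wears both sensor types, the Objective section hypothesises that the new sensors perform at least as well as the wired ones and lists adverse effects among the factors examined, and results from one iteration informed the next. A reader will set the two counts side by side. If part of each count is not irritation, that informal comparison concerns something other than what its name says.

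**Working it through.** There is no figure to reproduce. The documents state no irritation rate, no mark rate and no sample-size calculation for the skin outcome; the 80% power statement concerns the signal-quality variables.

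**Inputs from the documents:** the YES rule, the unfiltered numerator, the two post-removal inspections, and 40 participants (iteration 1) and 30 (iteration 2), each tested with both sensors.

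**Assumed inputs:** true irritation pW = 5% (wired) and pP = 15% (patch); harmless-mark rates mW and mP from 0% to 60%; marks and irritation independent.

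**Step 1, level.** P(YES) = 1 − (1 − p)(1 − m), so the overstatement of irritation is m(1 − p). For p = 5%:
- m = 2%: 0.02 × 0.95 = 1.9 points
- m = 10%: 0.10 × 0.95 = 9.5 points, so 5% is reported as 14.5%

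**Step 2, difference.** Patch minus wired = (1 − pW)(1 − mW) − (1 − pP)(1 − mP). With equal mark rates this is (1 − m)(pP − pW), which shrinks but cannot change sign.

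| Marks wired / patch | YES wired | YES patch | Difference (true: +10 points) |
|---|---|---|---|
| 0% / 0% | 5.0% | 15.0% | +10.0 |
| 2% / 2% | 1 − 0.95 × 0.98 = 6.9% | 1 − 0.85 × 0.98 = 16.7% | +9.8 |
| 10% / 10% | 14.5% | 23.5% | +9.0 |
| 30% / 30% | 33.5% | 40.5% | +7.0 |
| 60% / 60% | 62.0% | 66.0% | +4.0 |
| 30% / 20% | 33.5% | 32.0% | −1.5 |
| 30% / 10% | 33.5% | 23.5% | −10.0 |
| 10% / 30% | 14.5% | 40.5% | +26.0 |

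The ratio is more sensitive than the difference: 3.0 with no marks, 23.5/14.5 = 1.62 at 10%/10%, and 40.5/33.5 = 1.21 at 30%/30%.

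**Step 3, when the difference vanishes.** Setting the difference to zero gives mW = 1 − (1 − pP)(1 − mP)/(1 − pW). For mP = 0%, 10%, 20% and 40%, mW must reach 10.5%, 19.5%, 28.4% and 46.3%. Reversal needs wired marks above these values. It also depends on the assumed true gap: with irritation of 5% against 20%, marks of 30%/20% give 33.5% against 36.0%, still in the true direction.

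**Step 4, effect on counts.** Exact binomial enumeration for 5% against 15%, treating the two sensor counts as independent (a simplification, since they are paired), gives the chance that the patch count falls below the wired count:

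| Marks wired / patch | n = 40 | n = 30 |
|---|---|---|
| 0% / 0% | 4.0% | 5.8% |
| 30% / 30% | 22.1% | 24.2% |
| 30% / 10% | 80.9% | 76.5% |

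**The case against.** The case for leaving the rule alone has real substance. For a new skin-contact device, recording any visible change is sensitive and asks little judgement of the rater. The type is written down with each YES, so nothing is lost at source. The SAP's broader label already fits the wider rule, so part of the problem is inconsistent naming. No planned test is affected. All of this stands, and it keeps the point small. It does not remove it, because the reported figure still carries the narrower name and no tabulation by type is planned. Rater blinding ("This form was completed by a rater who was not part of the data collection process and who was blinded to sensors type") guards against biased scoring, but an imprint honestly recorded is still not irritation.

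Four stronger readings are tempting, and the documents do not support them:

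- **That the safety comparison is reversed.** Reversal needs the less irritating sensor to leave sufficiently more marks. No mark rates are given, equal rates only dilute, and unequal rates can exaggerate just as well.
- **That the sensors must mark differently because their adhesive areas differ.** No adhesive area is stated for either. The described differences in construction make unequal marking possible, not established.
- **That the recorded types and the 5-minute findings are left out of the incidence.** The text is silent on this; 5-minute YESs may well be counted.
- **That irritation should mean a change still present at 5 minutes.** Nothing in the documents supports that threshold. It would drop brief redness, although redness is the form's own example, and would lower the count for the investigators' own device after testing was done.

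**Conclusion.** The point holds as a matter of definition and reporting. The outcome is named as irritation, the event is any visible change, and the planned summary does not separate the two. If marks occur, the count overstates irritation by m(1 − p) and a descriptive sensor difference is diluted. If marks also differ by sensor, the difference can be exaggerated or reversed. In the illustrations above, a true 10-point difference appears as anything from −10 to +26 points, but at 2% marks under both sensors it is 9.8. Every rate used is an assumption, as is the independence of marks and irritation, so the size in this trial is unknown and may be negligible. The consequence is confined to the reading of a secondary outcome summarised by counts alone. It is a low-priority improvement.

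**What to change.** 1. Label the existing count *any visible skin change* and keep it.
2. Beside it, report the number of participants whose recorded type is a skin reaction, as opposed to an imprint or residue. Give this per sensor type and per iteration, separately for the immediate and the 5-minute inspections.
3. Make that classification from the recorded descriptions, without knowledge of sensor type.
4. Do not use persistence at 5 minutes as the sole definition of irritation; show both times.

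The cost is a few lines of SAP wording and one re-tabulation of data the form already collects. The downsides are a larger table with small cells (40 and 30 participants) and a post hoc sorting of free text, since the document describes testing in the past tense. Keeping the any-change count means no event disappears from the report, and readers can see how much the sorting matters. If marks were rare, the two sets of rows will nearly agree.

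### Does working out skin-irritation incidence from the number of YES marks count reactions twice or charge them to the wrong sensor?

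*Combined protocol and SAP*

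**What the plan says.** Under Secondary Outcome Variables – Preclinical parameters, the aim is put in terms of people: "Specifically, we documented the incidence of skin irritations in the subjects". A rater blinded to sensor type fills in a binary form. "For any irritation or change in appearance YES was selected", and the kind of irritation is described in words. The section also calls for the skin to be examined before as well as after each experiment. On timing it adds: "This inspection was completed immediately after removal of each sensor type and 5 minutes later as well". The counting rule is one sentence: "The number of YESs were used to calculate the incidence of these adverse effects in the sample".

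The Statistical Analysis Plan section adds only that skin effects are reported descriptively as frequency counts.

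Two design features bear on attribution. Both sensor types are tested in the submental area, and Design and Devices states: "There was a 10-min rest period between the two experimental conditions". The order of the sensors was counterbalanced (Instrumentation Validation – Data Collection), with 40 participants in the first iteration and 30 in the second.

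**The concern.** Three things are left unsaid.

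- **Unit.** Two post-removal checks per sensor allow two YES marks for one reaction. The plan does not say that a participant counts once, and it gives no denominator.
- **Baseline.** The earlier inspection is described, but its role in the calculation is not. A change in appearance implies a comparison with an earlier look; irritation of any kind does not.
- **Attribution.** The second set of tasks "was repeated 10 min after the first set with the other type of device", in the same region. Redness left by the first sensor might still be visible after the second is removed, and no rule says which sensor it belongs to.

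Skin inspection is the only safety measure described, and it is reported without a test, so the percentage is itself the result. If events are few, one reaction counted twice doubles its share of the figure. Carry-over between sensors could blur the comparison of the devices.

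**Working it through.** The documents give no skin-reaction rate, target or sample size for this outcome, so there is no stated figure to reproduce.

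**1. Unit**

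Inputs from the documents: n = 40 and n = 30; two post-removal checks per sensor.

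| Reading | Iteration 1 | Iteration 2 |
|---|---|---|
| One reaction, participant counted once | 1/40 = 2.5% | 1/30 = 3.3% |
| Same reaction at both checks, YES marks added, divided by participants | 2/40 = 5.0% | 2/30 = 6.7% |
| Same reaction, each check tabulated separately | 1/40 at each check | 1/30 at each check |
| Maximum YES marks per sensor | 2 × 40 = 80 | 2 × 30 = 60 |

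Only the second row inflates the result. That reading allows 80/40 = 60/30 = 200%, which cannot be an incidence among subjects. The plan's own description of the measure therefore argues against it. The first and third rows both fit the text.

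**2. Baseline and attribution: what is collected**

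The inspection section speaks of looking at the skin before and after each experiment. The ease-of-use paragraph that follows speaks of an experiment with each device, so an experiment plausibly means one sensor condition. On that reading there is an inspection just before the second sensor. If an experiment instead means the whole session, the first sensor's 5-minute check still falls within the 10-minute rest, provided the rest starts at or after removal. Either way, a lingering mark would probably be on record before the second sensor went on.

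**3. Carry-over: how large, and in which direction**

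Assumptions, none of them from the documents: equal order groups; independent reactions; each participant counted once per sensor; true rates pE for the patch and pC for the conventional electrodes; qE and qC the share of each sensor's reactions still visible after the other sensor is removed.

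If the earlier inspection is ignored:

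- rate_E = pE + (qC/2) × pC × (1 − pE)
- rate_C = pC + (qE/2) × pE × (1 − pC)

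With qE = qC = q, the difference reduces to (pE − pC)(1 − q/2). With pE = 0.20 and pC = 0.05, a true difference of 15 points:

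| qE | qC | rate_E | rate_C | Difference |
|---|---|---|---|---|
| 0 | 0 | 20.0% | 5.0% | 15.0 |
| 0.1 | 0.1 | 20.2% | 5.95% | 14.25 |
| 0.5 | 0.5 | 21.0% | 9.75% | 11.25 |
| 0 | 0.5 | 21.0% | 5.0% | 16.0 |

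The last row: rate_E = 0.20 + 0.25 × 0.05 × 0.80 = 0.21, and rate_C = 0.05. The gap widens, so carry-over does not always shrink the difference. The factor 1 − q/2 requires equal persistence for both devices.

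If the earlier inspection is used, so that a mark already present is not counted against the second sensor, and every such participant is conservatively treated as having no new reaction:

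- rate_E = pE − (qC/2) × pE × pC
- rate_C = pC − (qE/2) × pC × pE

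At qE = qC = 0.5: rate_E = 0.20 − 0.25 × 0.01 = 19.75%, rate_C = 0.05 − 0.25 × 0.01 = 4.75%, and the difference is 15.0 points. The ordinary baseline comparison removes the distortion in this example.

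**The case for a change.** The strongest reply is that the operative sentence counts YES marks, not people, and that with two checks per sensor the two give different numbers. A phrase about subjects hints at a unit without setting one. Counterbalancing and a blinded rater limit one-sided loading and rater bias, but they neither define the unit nor decide which sensor a lasting mark belongs to. The device is meant for later clinical use, so a safety percentage should have one meaning. A clarifying sentence would be cheap, because the forms are already complete.

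What stands: the wording is incomplete on all three points, and a reader of the plan alone cannot say with certainty how the percentage was formed. If the checks were in fact pooled, the unit part of the concern would be real.

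What does not stand is the step from incomplete wording to a defective analysis. Nothing in the documents shows pooled checks or counted pre-placement marks. The larger carry-over figures need reactions that outlast both the rest and the whole second set of tasks, no use of the earlier inspection, and equal persistence for both devices. The documents support none of these. A fuller remedy also has limits. First-period rates would rest on about 20 or 15 participants per sensor if the order groups were equal. Scoring a mark as worsened may not be possible from a YES/NO form with a short description.

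**Conclusion.** The concern does not call for a change. It identifies a counting convention left unwritten for a secondary, descriptive outcome in healthy volunteers, with no test, margin, alpha or power attached. The section's reference to incidence among subjects, the inspection before each experiment and the scoring of change point to the usual approach: one count per participant per sensor for a finding absent beforehand, over the participants exposed, with the two post-removal times distinguishable. An analyst would do this without being told.

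On that reading the double count is nil. On the literal pooled reading it is at most a factor of two (2.5% against 5.0%, or 3.3% against 6.7%, per reaction). Carry-over cannot be sized from the documents: it is zero if reactions fade before the second removal, can go in either direction if persistence differs between devices, and cancels from the difference when persistence is equal and the earlier inspection is used. This conclusion rests on the natural reading of the section and on an inspection, or the first sensor's 5-minute check, preceding the second sensor.

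### Does a power figure worded as detecting a difference undermine a plan that tests non-inferiority and equivalence?

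*Combined protocol and SAP*

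**What the plan says.** The Statistical Analysis Plan gives one power figure: "The study was designed to have at least 80% power to detect a difference in the primary variables of interest", which it lists as SNR and normalized mean amplitude. On sample size it adds "The sample size was determined via a power analysis based on pilot results", and on error control "Alpha level was set to .025 to correct for multiple comparisons".

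The tests are named a few lines later. "For S/N ratio comparisons non-inferiority tests were used for both" iterations, and "For the normalized amplitude data, equivalency testing was used for both" iterations. On margins: "Margins for these tests were calculated using our preliminary data acquired with the conventional electrodes". The only difference test named is for a secondary outcome: "Paired t tests were used to test for differences in satisfaction/comfort level".

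The Objective section gives the hypothesis that the new sensors "would have equal or better performance than traditional wired sEMG sensors used today in clinical practice". The Design and Devices section gives 40 participants for the first iteration and 30 others for the second, each tested with both devices.

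**The concern.** Power to detect a difference and power to show non-inferiority or equivalence are separate calculations. The first needs an assumed non-zero difference. If the devices are truly equal, a level-.025 difference test rejects 2.5% of the time at any sample size, which is simply its level. Non-inferiority or equivalence power is usually worked out at or near a true difference of zero, and it depends on the margin. A reader who takes the power sentence literally is told the power for a question that the primary analyses do not ask.

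A sample size derived for a difference could also be too small for equivalence. An iteration might then end inconclusively although the two devices perform alike. Nor does the SAP say whether the 80% refers to n=40, n=30 or both.

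**Working it through.** **The plan's own figure.** The 80% cannot be reproduced. The available inputs are n=40 and n=30 (Design and Devices), paired data (each participant uses both devices) and alpha .025 (SAP). The documents do not give the margins, the SD of the paired differences, the assumed true difference or the sidedness of alpha. A difference test also needs an effect size and an SD, so the figure would be just as uncheckable if the planned tests were difference tests. The missing inputs prevent the check; the wording does not.

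**What 80% power would require.** Assumptions: one value per participant and device, normally distributed paired differences, no order term, true difference 0. All margins are in units of the SD of paired differences.

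Normal approximation, .025 for each one-sided test:

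- Non-inferiority margin = (z(.975) + z(.80)) / √n = (1.960 + 0.842) / √n, which is 0.443 at n=40 and 0.511 at n=30.
- Equivalence margin (two one-sided tests) = (z(.975) + z(.90)) / √n = (1.960 + 1.282) / √n, which is 0.513 and 0.592.

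The exact calculation uses the noncentral t with n−1 degrees of freedom for non-inferiority, and integration over the sample SD for equivalence. Since sidedness is not stated, both readings of alpha are shown:

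| Margin for 80% power | n=40 | n=30 |
|---|---|---|
| Non-inferiority, .025 per side | 0.454 | 0.529 |
| Equivalence, .025 per side | 0.526 | 0.612 |
| Non-inferiority, .0125 per side | 0.504 | 0.589 |
| Equivalence, .0125 per side | 0.576 | 0.673 |

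**Power over a range of assumed margins** (.025 per side, true difference 0):

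| Margin | Non-inferiority, n=40 / n=30 | Equivalence, n=40 / n=30 |
|---|---|---|
| 0.4 | 69% / 56% | 39% / 16% |
| 0.5 | 87% / 75% | 74% / 51% |
| 0.6 | 96% / 89% | 92% / 78% |
| 0.7 | 99% / 96% | 98% / 92% |

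At 0.7 SD a floor of 80% holds for both tests at both sample sizes. At 0.4 SD it holds nowhere. The documents do not place the study's margins on this scale.

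**What a shortfall in power would do to the conclusions.** With .025 per side, the 95% interval for the paired difference has half-width t(.975, n−1)/√n in observed SDs: 2.0227/√40 = 0.320 and 2.0452/√30 = 0.373. An equivalence margin at or below that half-width cannot be met even if the observed difference is exactly zero. Low power therefore shows up as failure to establish equivalence or non-inferiority. It does not raise the chance of declaring a worse patch acceptable, because that error rate is set by alpha and the margin.

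**The case for a change.** The best argument for a change is that the mismatch can matter numerically and costs one sentence to remove. Suppose the sample size came from a two-sided .025 difference test with exactly 80% power. The detectable difference would be 0.504 SD at n=40 and 0.589 SD at n=30. If the margin equalled that difference and the devices were truly equal, non-inferiority power would be about 87% to 88% but equivalence power only about 75%, below the stated floor. With a true unfavourable difference of 0.1 SD, these fall to about 70% to 74% and 66% to 69%. A public SAP should let its readers check its only power claim.

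The arithmetic stands, and so does the observation that the sentence does not match the tests. The step to a defect does not. Nothing in the documents says that the calculation was for a difference or that the margin equalled the detectable difference. The SAP names the margin-based tests and says where the margins came from, so loose wording for a margin-based calculation fits the text at least as well. The thresholds are also hard to apply. They are in SDs of paired differences, whereas the margins come from conventional-electrode data and may be on another scale. The Data Collection section also describes several swallow types performed repeatedly, so the actual unit of analysis may differ from one value per participant.

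**Conclusion.** The wording is inconsistent, but no change to the plan follows. The phrase about detecting a difference does not describe the planned primary tests. Those tests do fit the hypothesis of equal or better performance, and an analyst following the SAP would run a non-inferiority test on S/N and an equivalence test on amplitude whatever the power sentence says. With testing complete, the confidence interval against the margin settles each comparison. That rule is what the planned tests already apply, so spelling it out would add nothing.

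Underpowering is not shown. On the illustrative assumptions, with one-sided tests at .025 and true equality, at least 80% power holds at both sample sizes when the margins reach 0.61 SD (equivalence) and 0.53 SD (non-inferiority). If .025 means .0125 per side, the corresponding margins are 0.67 and 0.59 SD. The unprinted margins, SD, assumed difference and sidedness are a reporting gap that would remain under any wording of the power sentence. Naming the two hypotheses in that sentence would read better, but it would leave the design, analyses and results as they are.
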